Unblinding of participants will only be performed when knowledge of the treatment allocation will influence participant management, for example, after overdose of the study treatment or placebo. Individuals not otherwise involved in the day-to-day conduct of the study will perform unblinding. In cases of emergency unblinding, each affected participant will be explained the reason for the unblinding and the potential risks incurred, and all communications will be

documented in affected participants' source documents within 24 hours of notification. The IRB will be notified immediately if such unblinding should occur.

Female patients must have a negative pregnancy test and agree to use effective contraception (or abstinence) during the course of the study. If a female subject becomes pregnant while taking part in this study, the subject will be withdrawn from the study. The subject's physician will be notified and the subject will be followed closely in conjunction with the subject's OB patient schedule through delivery or termination of pregnancy. Unblinding may occur by a member of the research staff so that the subject's physician and/or OB might know whether or not the active drug was in use.

12. Withdrawal from the Protocol

All participants will be informed as part of the consent process that their participation in the protocol is entirely voluntary and that they are free to discontinue at any time. Furthermore, such discontinuation will in no way prejudice any medical care they may be receiving from the institution or any clinician involved, or interfere in any way from their receiving on-going or future care.

If individuals elect to withdraw from the study, a termination visit will be scheduled, if possible, at which time the reason for their discontinuation will be solicited to allow appropriate action. If withdrawal is due to medical reasons, related or unrelated to the protocol, appropriate medical referral and follow-up will be recommended, which could include further safety visits until the event has passed. If individuals decline re-randomization/infusion of study drug at the 12 month visit, they will be allowed to remain in the study and asked to return for their regularly scheduled visits. Participants may be withdrawn from the study by the principal investigator if in his judgment continuation in the protocol would be detrimental to the health or safety of the participant, if the participant is not compliant, or if funding no longer exists for the project.

Although every attempt will be made to retain subjects in this study, we do not plan to replace withdrawn subjects in order to reach the enrollment of 60 subjects.

Additionally, unless a subject revokes his/her consent to use their health information (revokes HIPAA Authorization), any data collected prior to study withdrawal will be used in data analysis.

Female subjects who become pregnant will be withdrawn from the protocol and will not be allowed to continue participation.

13. Study Personnel

Roles and responsibilities of Key Study Personnel

[name], PhD: Principal investigator is responsible for overall management of all activities for this project. [name] will provide supervision and direction to the study coordinator for all clinical and regulatory aspects of the study, assist in recruitment, coordinate the randomization, do physical examinations and review the clinical status of participants with [name], be available to answer questions and evaluate changes in clinical status,

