Zoledronic acid has been shown by our group in a pilot study as well as by others in similar studies with limited numbers of participants after acute SCI to be able to prevent bone loss, at least over a 6 month period⁶⁹ and possibly as long as 12 months,⁷⁰ when changes in bone at the hip were analyzed. There has been no study of the effects of zoledronic acid beyond 12 months, nor has any study evaluated retreatment with this drug. Additionally, no studies have reported the effects of zoledronic acid on bone loss or bone strength at the knee, the site most frequently involved with fractures in people with chronic SCI.

Placebo

A matching solution containing the same diluent as the zoledronic acid will be available for infusion in those participants randomized to placebo treatment. The appearance and properties of

this solution will be identical to that containing the active treatment and all labeling will be identical other than participant identifier.

Calcium and vitamin D

Supplemental calcium and vitamin D will be provided to all participants. At study entry, all participants will have to have a normal serum 25-hydroxyvitamin D level, and we will provide cholecalciferol 1000 IU/day to all participants to assure normal levels during the course of the study. At this time, 1000 IU of vitamin D3 appears to be an adequate dose for maintenance of normal vitamin D levels.¹² If recommendations appear that indicate higher doses would be appropriate, treatment will be altered accordingly. For individuals who are already taking vitamin D supplements, the dosage of study cholecalciferol may be adjusted so as not to exceed 2000 IU per day, unless prescribed as such by the subject's primary physician.

All participants will be given supplemental calcium (1000 mg/day), provided as calcium carbonate, to be taken as 500 mg tablets, one tablet twice daily. For individuals who are already taking calcium supplements or obtain sufficient calcium through their diet, the dosage of study calcium may be reduced in order not to exceed 1000 mg of exogenous calcium per day. We recognize that there may be a preference for calcium citrate due to the lack of interference with absorption with concomitant use of proton-pump inhibitors, but our experience has been that calcium carbonate is well tolerated and does provide adequate calcium intake in most clinical settings.

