3.4. Randomization Method

This study contains two randomization points – one in the beginning of the study, and a re-randomization after 12 months. For the first randomization, participants will be assigned to treatment versus placebo in blocks of 2, 4, and 6. The order of the blocks of 2, 4 and 6 will be random. Within each block of sequential participants enrolled, half will be assigned to treatment and half will be assigned to the control condition, and the order of assignment will be at random. The randomization will be determined by a predetermined list, which will be created by an unblinded study personnel using a random number generator. The remainder of the study team and the participants will remain blinded to treatment throughout the course of the study. A copy of this list will be provided in a sealed envelope to the principal investigator in the event that treatment assignment needs to be known for a participant for safety reasons.

The second randomization will determine which treatment participants receive during the second year of their participation. The goal of this second randomization is to have 50% of the treatment group be randomized to continued treatment and 50% to be switched to placebo. Within the control group, 50% will be randomized to treatment and the other 50% will receive continued placebo. To achieve this, the unblinded personnel will create a random list of treatment versus control assignment using a random number generator. Participants will be assigned to treatment versus placebo in blocks of 2 and 4. With 60 subjects planning to be randomized, up to 15 subjects will be enrolled subjects in each of the following groups: zol/zol, placebo/zol, zol/placebo, and placebo/placebo.

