Subjects will all be in-patients or recently discharged from RIC/SRALab. Patients are not transferred to RIC/SRALab unless medically stable, but as the acute phase of their illness may have associated complications as well as requiring psychological adjustment; patients will be approached for inclusion into this study when deemed appropriate by their attending psychiatrist and/or nurse practitioner. If patients express an interest in the study, the study procedures will be explained, their questions answered, and the informed consent process as described in the preceding section will take place. Their medical record will be reviewed to assure they meet all inclusion and exclusion criteria. Assessments performed exclusively to determine eligibility for this study will be done only after obtaining informed consent. Assessments performed for clinical indications (not exclusively to determine study eligibility) may be used for baseline values even if the studies were done before informed consent was obtained.

There will be 10 visits for this study: Screening, Baseline, and 8 follow up visit at 3, 6, 9, 12, 15, 18, 21, and 24 months after baseline. It is desirable but not required for research subjects attend visits at 3, 9, 15, and 21 months after baseline. It is understood that based on where research subjects live and available transportation, visits every 3 months may not be possible. If a research subject cannot attend the follow-up visits at 3, 9, 15, or 21 months, the visit will be conducted over the phone and study supplements will be mailed to the research subject.

All patients will have their 25-hydroxyvitamin D levels measured at the screening visit if a recent test has not been done within the past 3 months. Those patients whose levels are lower than 20 ng/ml and are currently not on vitamin D will be dispensed a 7 day supply of vitamin D 50,000 IU. Infusion of study drug at baseline will only take place after a repeat 25-hydroxyvitamin D serum level meeting the study criteria will have been documented. Those patients whose levels are lower than 20 ng/ml but greater than or equal to 15 ng/ml and are currently on at least vitamin D 1,000 IU daily will be eligible for the study and will not need a repeat 25-hydroxyvitamin D serum level prior to infusion.

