Baseline Visit: Prior to infusion, it will be verified that all subjects are well-hydrated and have acceptable renal function and serum calcium levels (and a negative pregnancy test if appropriate). Subjects will be pre-medicated with acetaminophen, 650 mg orally, up to 4 hours prior to the infusion.

The study medication for the infusion will be provided by either the in-patient pharmacy or the study team who will have received blinded medication and will allocate active drug or placebo as indicated by the randomization scheduled in a sequential manner. The subject and the investigator/ investigator's staff will be blinded to treatment allocation. Study drug will be given at minimum over 15 minutes as an intra-venous infusion according to standard instructions in the package insert. Subjects weighing less than 40 kg will receive a reduced dose of study drug or placebo. Those assigned to the active study arm will received 2 mg of study drug diluted in 40 mL of saline. Those assigned to the placebo arm will receive 40 mL of saline. Subjects will be allowed to self-medicate post-infusion with 650 mg acetaminophen every 6 hours, up to 2600 mg per day, for up to 3 days.

Screening Visit

- Informed consent process
- Medical history
- Concomitant medications
- Urinalysis
- Pregnancy test (if applicable)
- Labs (CBC, Comprehensive Chemistry Panel, 25-OH vitamin D, TSH)
- Questionnaires (SCIM and SCILI)
- Walking Index
- Physical exam (if done at baseline visit, must be done prior to infusion)
- Vital signs
- Serum bone markers (can also be done at the baseline visit, but prior to study drug infusion)
- DXA (can be done at baseline visit)
- CT of knee and hip (can be done at baseline visit)

Randomization/Infusion (Baseline)

- Provide calcium and vitamin D
- Collect adverse events

- Review concomitant medications
- Vital signs (must be done prior to infusion)
- Physical Exam, with an oral examination (must be done prior to infusion)
- Labs (CBC, Chemistry Panel, 25-OH vitamin D, TSH) to be done prior to infusion. It should be verified that subject has an acceptable renal function, serum calcium concentration and 25-OH vitamin D prior to infusion.
- Urinalysis (must be done prior to infusion)
- Negative pregnancy test, if applicable (must be done prior to infusion)
- Serum bone markers (must be done prior to infusion)
- DXA and CT of knee and hip (must be done prior to infusion)
- Pre-treatment with acetaminophen (0-4 hours prior to infusion)

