- Verification that subject is well-hydrated (subject should drink 1-2 full glasses of water 0-4 hours prior to infusion)
- IV infusion of study drug

Follow-up Phone Call (or Visit if still inpatient at RIC/Shirley Ryan AbilityLab) (1-7 days after IV infusion)

- Collect adverse events

Follow-up Visits (Months 3, 6, and 18)

- Provide calcium and vitamin D
- Collect adverse events
- Review concomitant medications
- SCILI
- Walking Index
- Vital signs
- Serum bone markers
- DXA and CT of knee
- CT of hip at Month 6
- Month 6: Subjects with DXA BMD loss \geq 20% from baseline on at least two sites will be offered infusion with opposite treatment.

2nd Infusion (Month 12, or potentially Month 6)

- Provide calcium and vitamin D
- Collect adverse events
- Review concomitant medications
- Vital signs (must be done prior to infusion)
- Physical Exam, with an oral examination (must be done prior to infusion)
- Chemistry Panel (or at minimum serum calcium and creatinine) and if applicable, a negative pregnancy test (must be done prior to infusion). Lab workup done at an outside institution/lab is acceptable as long as it is completed within 3 months prior to the infusion.
- Serum bone markers (must be done prior to infusion)
- DXA and CT of knee and hip (can be done after the infusion)
- Pre-treatment with acetaminophen (0-4 hours prior to infusion)

- Verification that subject is well-hydrated (subject should drink 1-2 full glasses of water 0-4 hours prior to infusion)
- IV infusion of study drug

Follow-up Visits (Months 9, 15, and 21)

- Provide calcium and vitamin D
- Collect adverse events
- Review concomitant medications
- Vital signs
- Walking Index
- SCILI

Final Study Visit (Month 24)

- Collect adverse events
- Review concomitant medications
- Vital signs
- Walking Index
- SCILI
- Serum bone markers
- Labs (Chem Panel, CBC, and urinalysis)
- DXA
- CT of knee and hip
- Physical Exam

Event	Screening	Baseline	Follow-Up							
			Mo 3	Mo 6	Mo 9	Mo 12	Mo 15	Mo 18	Mo 21	Mo 24
Study Day		0	Mo 3	Mo 6	Mo 9	Mo 12	Mo 15	Mo 18	Mo 21	Mo 24
Visit #	V1	V2	V3	V4	V5	V6	V7	V8	V9	V10
Procedures:										
Informed Consent	X									
Demographic Data	X									
Questionnaires	X		X	X	X	X	X	X	X	X
Walking Index	X		X	X	X	X	X	X	X	X
Physical Exam	X			X*		X				X
Height	X									
Weight	X									
Vital Signs	X	X	X	X	X	X	X	X	X	X
AE Assessment		X	X	X	X	X	X	X	X	X
Incl/Excl Criteria	X									
Review con. meds.	X	X	X	X	X	X	X	X	X	X
Pre-treatment		X		X*		X				

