Study Drug Infusion		X		X*		X				
Dispense calcium		X	X	X	X	X	X	X	X	
Dispense vitamin D		X	X	X	X	X	X	X	X	
DXA		X	X	X		X		X		X
CT of Knee		X	X	X		X		X		X

CT of Hip		X		X		X				X
Labs:										
CBC	X									X
Chemistry Panel	X			X ^{*a}		X ^a				X
25-OH Vitamin D	X									
TSH	X									
Urinalysis	X									X
Pregnancy Test	X			X [*]		X				
Bone Markers		X	X	X		X		X		X

X* - Month 6: Subjects with DXA BMD loss \geq 20% from baseline on at least two sites will be offered infusion with opposite treatment. In such cases, infusion-related assessments to be done at the 12 month visit will be done at the 6 month visit instead.

X^a – At minimum, a serum calcium and creatinine is required before an infusion.

8. Compensation for Participants

Visit #	Amount of Stipend	Payment Type
1 – Screening	\$0	Cash
2 – Baseline	\$50	Cash
3 – Month 3	\$50 + \$25 (travel)	Cash
4 – Month 6	\$50 + \$25 (travel)	Cash
5 – Month 9	\$25 (travel)	Cash
6 – Month 12	\$50 + \$25 (travel)	Cash
7 – Month 15	\$25 (travel)	Cash
8 – Month 18	\$50 + \$25 (travel)	Cash
9 – Month 21	\$25 (travel)	Cash
10 – Month 24	\$50 + \$25 (travel)	Cash
Unscheduled Visit	\$25 (travel)	Cash
TOTAL	\$525	

Study payments will be given to participants in cash at the time of each study visit. Participants will only be paid for study visits that are completed. Once discharged from RIC/Shirley Ryan AbilityLab, a travel stipend of \$25 will be given at each completed study visit on site. This travel stipend is meant to cover the expenses of travel to and from site. For incurred travel expenses greater than \$25, subject will be reimbursed via check instead of \$25 cash.

In addition, when necessary, travel arrangements will be made to assist participants in returning to the site for important study time points (Month 6, Month 12, Month 18, and Month 24 visits). This may include reimbursement for mileage, rental car services, taxis, airfare, etc. In these cases, the additional travel stipend of \$25 will not be given to subject.

9. Data Management

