Radiation Exposure: Risks of radiation exposure will be listed in the study consent form per the Radiation Safety Officer's assessment based on DXA and CT imaging.

Vitamin D and calcium. The doses administered in this study are significantly below the safe upper limit defined by the Institute of Medicine's recent report.^{3,4} Overdose of either can result in hypercalcemia, which is associated with nausea and vomiting, loss of appetite, excessive thirst, constipation, abdominal pain, muscle weakness and pain, confusion, lethargy and fatigue.

Risk management and emergency response

To mitigate the risks associated with the infusion of zoledronic acid, individuals with renal insufficiency (estimated creatinine clearance of ≤ 35 ml/min) and those having low serum calcium levels will be excluded from the study. Additionally, normal serum levels of vitamin D will also be required prior to the baseline infusion and all infusions will be done over 15 minutes to reduce the possibility of exposure to high serum levels of zoledronic acid (15 minutes is the minimum recommended time for infusion). All participants will be pre-medicated with acetaminophen 650 mg at 0-4 hours prior to infusion of zoledronic acid and then every 6 hours thereafter for up to 3 days as needed to reduce the incidence of the acute flu-like response (low grade fever, myalgias, joint aches) that can occur. An oral examination will be performed prior to study entry to exclude individuals with poor dental hygiene or in need of invasive dental procedures. Female patients will have to have a negative pregnancy test to be enrolled in the study and agree to use effective contraception (or abstinence) during the course of the study.

Participants will be told to call the research coordinator or principal investigator if at any time in the study they have a change in their medical condition, particularly if they believe this may be related to the study interventions. They will be given a telephone number to call that will reach a study member at any time (24 hours/day) during the course of the study.

Potential benefits

The possible benefits include reduction in the loss of bone mass and bone strength that occurs during the months after acute SCI; this may result in a reduction in the future risk of bone fractures. Taking part in this study may also help scientists to better understand bone loss after acute SCI and may help inform future research studies about bones.

11. Unblinding Procedure

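### The vitamin D check and the requirement that labs be verified as acceptable apply only to the baseline infusion, so up to 15 placebo/zol participants get their first zoledronic acid at month 12 without a repeat level

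*Protocol*

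**What the plan says.** **Before the baseline infusion.** Protocol Section 7 (Study Procedures) deals with patients below 20 ng/ml who are not on vitamin D. They get a 7-day supply of 50,000 IU, and "Infusion of study drug at baseline will only take place after a repeat 25-hydroxyvitamin D serum level" meeting the criteria is on record. The Randomization/Infusion (Baseline) list adds: "It should be verified that subject has an acceptable renal function, serum calcium concentration and 25-OH vitamin D prior to infusion". Section 10 (Risk management and emergency response) names this as a safeguard: "normal serum levels of vitamin D will also be required prior to the baseline infusion".

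**Before the second infusion (month 12, or month 6 after a switch).** The Section 7 list asks for a chemistry panel, or at least calcium and creatinine, a pregnancy test where applicable, and confirmation of hydration. It does not mention 25-OH vitamin D, and it does not say that the results must be acceptable. It also states: "Lab workup done at an outside institution/lab is acceptable as long as it is completed within 3 months prior to the infusion". The schedule of events marks 25-OH vitamin D at screening only, and its footnote reads: "At minimum, a serum calcium and creatinine is required before an infusion". For a month-6 switch, the month-12 infusion assessments are moved forward to month 6.

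**Who receives active drug at the second infusion.** Section 3.4: "Within the control group, 50% will be randomized to treatment and the other 50% will receive continued placebo". The planned size of the placebo/zol group is up to 15.

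**Supplements.** Section 3.3: "we will provide cholecalciferol 1000 IU/day to all participants to assure normal levels during the course of the study". Calcium is supplied as well.

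**The concern.** Section 10 puts acute renal failure and hypocalcemia first among the risks of zoledronic acid. It answers them with entry limits on renal function and calcium, normal vitamin D and a minimum infusion time. For a participant who starts on placebo, the full set of laboratory checks comes before an infusion that contains no drug. The shorter set comes before the first real exposure.

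If the second-infusion list is followed as written, a placebo/zol participant can receive a first dose of zoledronic acid on a calcium and creatinine result from three months earlier, with no current vitamin D level. The schedule has no chemistry panel between screening and month 12 except for a month-6 switch, so that outside result may be the only one since study entry. The documents give no reason for treating the two infusions differently. What is at stake is participant safety.

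**Working it through.** **1. The two infusions side by side**

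| Item | Baseline infusion | Second infusion |
|---|---|---|
| 25-OH vitamin D | Required and verified | Not listed |
| Calcium, creatinine | Required and verified as acceptable | Required, no acceptance limits stated |
| Age of results | No outside-lab allowance stated | Up to 3 months if from an outside lab |
| Hydration | Verified | Verified |
| Supplements beforehand | May be none | Supplied since baseline |

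**2. The plan's own group size.** Inputs: 60 randomized, half to placebo (Section 14.1), and half of those re-randomized to zoledronic acid (Section 3.4).

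60 × 0.5 × 0.5 = 15, which matches the planned placebo/zol size.

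**3. Drop-out.** Section 14.3 expects less than 20%. At 20%: 15 × 0.8 = 12.

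**4. Share of first exposures.** 30 at baseline + 15 at month 12 = 45, and 15/45 = 33% come without a repeat vitamin D level. If drop-out removes 20% by month 12: 12/(30 + 12) = 29%.

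**5. Month-6 switches.** Section 10 offers the opposite treatment at month 6 to anyone who has lost 20% or more at two or more sites, and does not re-randomize them. Suppose *k* placebo participants switch and nobody drops out:

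- first dose at month 12: (30 − *k*)/2
- first dose at either time after baseline: *k* + (30 − *k*)/2 = 15 + *k*/2

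| *k* (assumed) | At month 12 | Total after baseline |
|---|---|---|
| 0 | 15 | 15 |
| 6 | 12 | 18 |
| 30 | 0 | 30 |

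The documents give no expected *k*, so the range is 15 to 30.

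**6. Age of the last vitamin D level at month 12.** If drawn at baseline: 12 months. If Section 7's allowance for a test up to 3 months before screening was used and not repeated: 12 + 3 = 15 months, plus the screening-to-baseline interval. The second figure is a worst case, because the baseline list also names the test.

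**7. What cannot be computed.** The documents do not give the proportion of supplemented participants who would be below the cut-off, or the proportion who would use an outside lab. The number at actual risk is therefore unknown.

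**The case against.** The case on the other side has substance.

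- **The plan is consistent.** Every relevant section says the same thing: settle vitamin D before baseline, maintain it with supplements, and check calcium and creatinine before each infusion. No document sets a standard that calls for a repeat level before a second annual dose. This stands, so the point is a safety judgement and not a contradiction in the plan.
- **Risk at month 12 differs from risk at baseline.** Calcium and vitamin D are dispensed from baseline through month 21 and mailed when a visit is by phone. Calcium and creatinine, the most direct checks on the two named risks, stay mandatory. This also stands. It lowers the risk, but no scheduled level shows that it has worked, and the visit lists name no check of supplement adherence.
- **The protocol accepts 15 ng/ml on supplements.** A reader might infer from the separate rule for patients at 15 to below 20 ng/ml that the plan concedes 1,000 IU a day to be inadequate. It does not. Section 4.1.1 counts 15 or more as normal for someone taking at least 1,000 IU daily, and no document suggests how many would fall below that.

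Three further readings go too far. It is tempting to say that these participants are dosed with no vitamin D level at all, but each has a qualifying screening or baseline value, and what is missing is a repeat. One might also assume that all 15 would have three-month-old chemistry. That is a permitted maximum for outside labs only, and the schedule places a chemistry panel at month 12. Finally, one could count all 30 planned active infusions at month 12 as unprotected. Half of those are zol/zol participants who have already had one active dose after the full baseline check, so the argument about first exposure applies to 15.

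**Conclusion.** The concern holds as a safety gap of limited size. Up to 15 placebo/zol participants, about 12 with 20% drop-out, receive their first zoledronic acid without a repeat 25-OH vitamin D level. They do so under a lab rule that permits outside calcium and creatinine results up to 3 months old and states no acceptance limits. Any placebo participant switched at month 6 is in the same position, which raises the total to 15 + *k*/2.

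This assumes the planned 1:1 splits and full uptake of the second infusion. Section 12 lets participants decline it, which would lower the count. The documents do not show that anyone would be deficient or harmed. The 12-month efficacy comparison, the sample size and the power are unaffected. The change is still worth making because it is cheap and addresses the risks the protocol itself ranks as most serious.

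**What to change.** Amend the second-infusion list and the schedule of events in Section 7, and the matching sentence in Section 10. Apply the change to all participants in both arms so that blinding is kept.

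1. Require serum calcium and creatinine, with estimated clearance, within about 30 days before the second infusion, from any lab. Results must meet the Section 4.1.1 limits: normal calcium, creatinine below 2.0 mg/dl, clearance above 35 mL/min. Thirty days is a judgement, not a figure from the documents.
2. Add one 25-OH vitamin D result to the same pre-infusion workup, drawn early enough for the result to be back. Use the Section 4.1.1 cut-off: at least 15 ng/ml if taking at least 1,000 IU daily, otherwise at least 20. Month 9 is not a ready-made time for it, since no blood is drawn then and the visit may be by phone.
3. State a repletion-and-repeat step that covers participants already on supplements. The existing route in Section 7 covers only patients who are not on vitamin D, so it cannot simply be cited.
4. Apply the same rules to the month-6 switch.

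**Cost.** Up to 60 vitamin D assays (60 × 0.8 = 48 with 20% drop-out), some repeat chemistry, a few delayed infusions and the wording changes. The SAP Overview describes both randomizations in the past tense, so the change helps only participants still awaiting a second infusion. If none remain, state the missing repeat level as a limitation when reporting placebo/zol safety.
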